6. ETHICAL CONSIDERATIONS

6.1 Regulation statement

The study will be conducted according to the principles of the Declaration of Helsinki.

6.2 Recruitment and consent

Because there is no patient randomization, the project does not change the regular patient care. Patients will be informed about the evaluation of routine endoscopic treatments and the need to collect objective data in a standardized fashion. Informed consent will be obtained in an anonymous register and include the routine clinical parameters. Based on our previous experience with clinical trials, we assume that most patients will agree on data collection, but in case of drop-outs, the inclusion period may need to be extended.

Participating endoscopists inform the patients about the trial and will give them an information package including the patient information folder (PIF), an informed consent form, a Quality-of-Life questionnaire and a return envelope. The endoscopists place a comment in their endoscopy report regarding having informed the patient about the study. Furthermore, the endoscopists note the patient's information in the patient identification log.

Patients can send their informed consent form and QoL-questionnaire to the executive researcher (PhD student) when they want to participate in the questionnaire study.

6.3 Benefits and risks assessment, group relatedness

The project does not change the regular patient care, so there are no additional risks from this study, compared to the standard care.

The outcome of this project will clearly benefit our patients (fewer colonoscopy follow-up examinations and fewer surgical resections). We also expect that implementation of the new endoscopic resection techniques in practice will improve patient's quality of life. Importantly, the reduced number of unnecessary procedures will enable a better utilization of colonoscopy resources in the context of the national population screening program.

6.4 Compensation for injury

The project does not change the regular patient care, so there is no obligation to provide insurance.

7. ADMINISTRATIVE ASPECTS, MONITORING AND PUBLICATION

7.1 Handling and storage of data and documents

Participating endoscopists will keep a patient identification log at the site.

An electronic case report form (eCRF) will be used to collect the data (i.e. indication for colonoscopy, colonoscopy findings, endoscopic resection technique used, local recurrence rate, number of repeat colonoscopies, complication rate, and number of referrals to surgery). Informed consents and QoL-questionnaires will be send to the executive researcher by the patients and will be stored in Maastricht.

An external PhD-student (executive researcher) will collect the data in the eCRF. Data collection and storage will be done in Castor Data Management System.

7.2 Monitoring and Quality Assurance

There will be no monitoring.

7.3 Amendments

Amendments are changes made to the research after a favourable opinion by the accredited METC has been given. All amendments will be notified to the METC that gave a favourable opinion.

7.4 Annual progress report

The sponsor/investigator will submit a summary of the progress of the trial to the accredited METC once a year. Information will be provided on the date of inclusion of the first subject, numbers of subjects included and numbers of subjects that have completed the trial, serious adverse events/ serious adverse reactions, other problems, and amendments.

7.5 Temporary halt and (prematurely) end of study report

The investigator/sponsor will notify the accredited METC of the end of the study within a period of 8 weeks. The end of the study is defined as the last patient's last visit.

The sponsor will notify the METC immediately of a temporary halt of the study, including the reason of such an action.

In case the study is ended prematurely, the sponsor will notify the accredited METC within 15 days, including the reasons for the premature termination.

Within one year after the end of the study, the investigator/sponsor will submit a final study report with the results of the study, including any publications/abstracts of the study, to the accredited METC.

7.6 Public disclosure and publication policy

The intellectual property rights pertaining to training materials created within the framework of this project will be owned by the project leader. Part of the training materials (photo documentation, powerpoint slides) will be provided by international experts in this field and thereby remain their intellectual property, in accordance with national and international law on authorship {World Intellectual Property Organization, 1979}. The rights to use these materials in the Dutch training program will be granted. There will be no conflicting contracts preventing from publication and implementation of the training program that will be developed during this study.

- b. Zoom
- c. Zoom with advanced imaging modality (e.g. NBI, I-scan)

STEP 2: ENDOSCOPIC MUCOSAL RESECTION

1. EMR documentation in endoscopy report

- a. Lifting fluid → NaCl / Gelofusin/ Venofundin

- b. Dye included in the injection fluid →yes/no
- c. Adjuvant adrenalin in lifting fluid → yes/no?
- d. En-bloc or piecemeal?
- e. Number of pieces [n = ... / >10 fragments]
- f. Intraprocedural bleeding yes/no?
 - i. Number of intraprocedural bleedings
 - ii. Treatment intraprocedural bleeding
 - 1. Clipping
 - 2. Snare tip coagulation
 - 3. Coagulation grasper
 - 4. Adrenalin injection
- g. Residual tissue after EMR yes/no?
 - i. In case of residual tissue, adjunctive treatment?
 - 1. Cold avulsion with biopsy forceps
 - 2. Cold avulsion with thermal ablation (CAST)
 - 3. Hot avulsion
 - 4. Snare tip coagulation
 - 5. Suck and snare
 - 6. APC
- h. Adjuvant treatment performed to prevent recurrence yes/no?
 - i. Argon plasma coagulation
 - 1. Borders (y/n)
 - 2. Scar surface (y/n)
 - ii. Snare tip soft coagulation
 - 1. Borders (y/n)
 - 2. Scar surface (y/n)

2. Tattoo 2 cm distal at the same side (to make sure the scar can be retrieved during surveillance colonoscopy)

3. Photo/videodocumentation

- a. Recording first 5 EMRs (intervention group)
- b. Photodocumentation of the scar
 - i. Before adjunctive treatment
 - ii. Before adjuvant treatment
 - iii. After adjuvant treatment

STEP 3: AFTER COLONOSCOPY

- 1. Informing the patient about the study

2. Providing the information package
3. Note patient data on study list (patient number, sex, birthdate)
4. Schedule 6 month FU colonoscopy

STEP 4: SURVEILLANCE COLONOSCOPY AFTER 6 MONTHS

1. Endoscopy report

- a. Recurrence yes/no?
- b. Unifocal or multifocal [n]
- c. Size of largest recurrence (in mm)
- d. In case of recurrence, treatment yes/no?
 - i. Re-EMR
 - ii. Cold avulsion
 - iii. Cold avulsion with snare tip coagulation (CAST)
 - iv. Hot avulsion
 - v. Suck and snare
 - vi. eFTR
 - vii. ESD
 - viii. APC
 - ix. Snare tip soft coagulation (STSC)

2. Biopsy the scar

- a. Take a biopsy every 5 mm [e.g. in a scar of 18mm, 3 biopsies are taken]
- b. Present every biopsy in a separate PA jar

3. Photodocumentation

- a. Scar [white light, zoom and advanced imaging modality]

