4.3.4 Data inclusion

All endoscopists will perform at least 35 consecutive endoscopic resections of LNPCPs. During the procedure, a tattoo will be placed 2 cm distal of the lesion at the same side, to make sure the scar can be found during the surveillance colonoscopy. Six months follow-up data will be collected for all cases. During this surveillance colonoscopy, endoscopists are asked to report whether there is recurrence and how this is treated. In addition, the scar will be photo documented in white light and zoom with advanced imaging (e.g. NBI, I-scan, blue light). Furthermore, the scar will be biopsied, with one biopsy every 5 mm (with the biopsies being presented to the pathology in separate jars).

Beyond this project proposal, we will monitor long-term (36 months) outcomes after endoscopic resection (i.e. local recurrence, referral to surgery). LNPCP patients will receive surveillance colonoscopy according to the Dutch post-polypectomy surveillance guideline {Dekker, 2013}.

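### The checklist has the unblinded endoscopist list each case after the EMR, and no check of completeness is described, so selective listing by arm could go unseen

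*Protocol*

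**What the plan says.** Section 4.2 randomises centres. Both groups receive the optical-diagnosis e-learning, and only the intervention group receives the EMR package; under 4.3.2 that group also records its first five EMRs on video. Every endoscopist therefore knows the arm before any study patient is identified.

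Appendix A orders the work. Step 1 is lesion assessment. Step 2 is the EMR, where en-bloc or piecemeal resection, number of pieces, bleeding and residual tissue are recorded. Then comes "STEP 3: AFTER COLONOSCOPY", which covers informing the patient, handing over the package and this item: "Note patient data on study list (patient number, sex, birthdate".

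Section 6.2 names the same person for these tasks: "Participating endoscopists inform the patients about the trial and will give them an information package", and "the endoscopists note the patient's information in the patient identification log". Section 7.1 places the log locally: "Participating endoscopists will keep a patient identification log at the site". Section 7.2 says "There will be no monitoring".

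Two rules limit discretion. Section 4.3.4 says "All endoscopists will perform at least 35 consecutive endoscopic resections of LNPCPs" and asks for six-month data on all cases. Section 4.3.1 requires a standard parameter set in the report of each colonoscopy in which an LNPCP is found or removed. Section 7.1 has an external PhD student enter the eCRF data. No section describes comparing the study list with endoscopy or pathology records.

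Section 4.3.3 also describes a two-step pathway. If the lesion is not resected at the index colonoscopy, the first questionnaire is given after that procedure and so before the resection.

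**The concern.** When clusters are randomised and patients are identified afterwards by staff who know the allocation, randomisation no longer protects the mix of patients in each arm. Here the checklist goes a step further: the operator makes the entry after seeing how the resection went, and what the operator has seen predicts the primary endpoint. Section 2 cites an odds ratio of 4.39 for recurrence after piecemeal rather than en-bloc resection.

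If cases with a poor procedural result were listed less often in one arm, the six-month recurrence comparison would be biased. The primary model (5.1) contains study group, previous experience, SMSA score and a random intercept per colonoscopist. SMSA covers size, morphology, site and access, so it would partly handle selection on lesion difficulty. It does not cover intraprocedural results such as fragmentation or residual tissue. A random intercept does not remove a shift shared by a whole arm.

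**Working it through.** **1. The plan's own figure, to obtain an effective sample size.** Inputs from 3.1.4: 20% vs 10% recurrence, power 90%, alpha 5% (two-sided assumed), ICC 0.025, m = 35, 10% efficiency loss, 20% drop-out.

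- Two-proportion formula without continuity correction: 266 per group.
- Design effect: 1 + (35 − 1) × 0.025 = 1.85.
- 266 × 1.85 / 0.90 / 0.80 = 683.5, which matches the stated 683.
- Effective n per arm: 683 × 0.80 × 0.90 / 1.85 = 265.8.

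The false-positive rates below come from the two-sided normal-approximation test at this effective n, which is held fixed for simplicity.

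**2. What the scenarios assume.** No true training effect, and omission in the trained arm only. The documents give no omission share, no direction and no piecemeal share; all three are assumptions. The recurrence inputs are from section 2: piecemeal 20% (95% CI 16–25%) and odds ratio 4.39.

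**3. Scenario A: omitted cases at the upper confidence limit.** Overall rate 20%, with 10% of cases omitted at 25% recurrence:

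(0.20 − 0.10 × 0.25) / 0.90 = 0.175 / 0.90 = 19.4%

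The shift is 0.6 points and the false-positive rate is about 5.3%.

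**4. Scenario B: omission by piecemeal status.** The piecemeal odds are 0.20/0.80 = 0.25. The en-bloc odds are 0.25/4.39 = 0.0569, which is a risk of 0.0569/1.0569 = 5.4%. With piecemeal share s and a fraction f of piecemeal cases omitted:

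- true rate = s × 0.20 + (1 − s) × 0.054
- apparent rate = [s(1 − f) × 0.20 + (1 − s) × 0.054] / (1 − s f)

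| s | f | true rate | apparent rate | shift (points) | false-positive rate |
|---|---|---|---|---|---|
| 50% | 25% | 12.7% | 11.7% | 1.0 | 6.6% |
| 66% | 25% | 15.0% | 14.1% | 1.0 | 6.2% |
| 80% | 25% | 17.1% | 16.4% | 0.7 | 5.6% |
| 50% | 50% | 12.7% | 10.3% | 2.4 | 14.2% |
| 66% | 50% | 15.0% | 12.6% | 2.5 | 12.9% |
| 80% | 50% | 17.1% | 15.1% | 2.0 | 9.4% |

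The underlying rate in this scenario is 12.7% to 17.1%, not the planning value of 20%. The share of all cases omitted is s × f, from 12.5% (50% × 25%) to 40% (80% × 50%), so the lower rows describe heavy omission.

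**5. Against the planned effect.** The target difference is 10 points. Shifts of 0.6 to 2.5 points are 6% to 25% of it.

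**The case against.** The strongest reply is that the inclusion rule leaves no room for choice: consecutive resections, six-month data for all cases, no exclusion criteria (3.1.3), a standard report for every LNPCP, and an outside student entering the data. That is right about the rule. What is missing is any described way to see whether it was followed, and 7.2 rules out monitoring, which might have shown it.

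Four stronger readings are tempting, and the documents do not support them.

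- **Patients are reached only after resection.** This fits the Appendix A checklist and resection at the index colonoscopy. In the two-step pathway of 4.3.3 the approach may come earlier, because 6.2 puts the questionnaire in the information package. It still comes after randomisation and, per 6.2, from the participating endoscopist.
- **Unlisted cases are replaced by recruiting longer.** Section 6.2 says "in case of drop-outs, the inclusion period may need to be extended", in a sentence about patients agreeing to data collection. It states no replacement of unlisted cases.
- **The model does nothing about selection.** SMSA adjustment handles part of any selection on lesion difficulty. Selection on intraprocedural results is what escapes.
- **Omitted cases would recur at 40% to 50%.** No section gives such a rate for any subgroup. The resection-status figure available is 20% (16–25%) for piecemeal resection.

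Two further objections stand in part. Identification after allocation is hard to avoid in a trial of trained operators, so the aim is to make the listing checkable. The direction is also open: omission in the control arm would mask a true benefit, and similar omission in both arms would largely cancel.

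**Conclusion.** The point holds as a weakness in how cases enter the trial. The arm-aware operator lists the case after the EMR under Appendix A, and no check of the list is described. The documents show that selective listing could happen unseen; they do not show that it does.

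On inputs taken from section 2, the bias is small to moderate: about 0.6 points in scenario A and 0.7 to 2.5 points in scenario B, where the false-positive rate rises from 5% to about 6% to 14%. These figures rest on assumed omission shares, an assumed piecemeal share of 50% to 80%, omission in the trained arm only and no true effect. The change is worth making because it is cheap and because cases that never reach the data set cannot be recovered in the analysis.

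**What to change.** 1. In Appendix A, move the study-list entry from Step 3 to Step 1, so that each LNPCP planned for resection is listed before the resection starts. This covers both pathways.
2. In 7.1, have the PhD student who already collects the data reconcile each endoscopist's list against the dated endoscopy reports required by 4.3.1. Eligible resected cases that were not listed should be added where data use is permitted.
3. Report eligible, listed and analysed counts by arm, with listed lesions that were never resected counted separately so that the denominators stay comparable.

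The cost is one reordered checklist line and modest extra work for the PhD student. Patient care, endpoint and sample size do not change. The operator still makes the entry, and an entry due during the procedure could be completed late, so the reconciliation in item 2 is the main safeguard.
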